## 7.3 Statistical analysis

Data will be entered into a validated eCRF developed by ICTU. Continuous variables will be presented as means and standard deviations if normally distributed, and as medians and inter-quartile ranges for skewed data, whilst categorical variables will be presented as frequencies and percentages. Normality will be checked, and appropriate transformation performed if not normally distributed. All statistical tests will be two-tailed with a 5% significance level.

A detailed description of all the analyses will be given in the statistical analysis plan (SAP) that will be prepared and finalised prior to database lock. Any deviations from the SAP will be justified and documented in the final report.

### (i) Analysis populations

The primary analysis will be performed according to the intention to treat principle, including all participants who are randomised to a study arm, according to their allocated arm, regardless of treatment received.

Per-Protocol (PP) populations will also be defined:

Those who received CSP as per adjudication

Those who received His bundle pacing as per adjudication

Those who received Left bundle pacing as per adjudication

Those who received selective His bundle pacing as per adjudication

Those who received non-selective His bundle pacing as per adjudication

Those with an EF <50% at enrolment

Those with an EF >50% at enrolment

Those with a mean pacing percentage >20% during the trial

Those with a mean pacing percentage >40% during the trial

Those with a mean pacing percentage >80% during the trial

Those with AF at baseline

Those with complete AV block at baseline

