#### (i) Inclusion criteria

- Adults aged 18 or above with
- Left ventricular ejection fraction >35% from any clinical echocardiogram (including MRI and V scan if ECHO cannot be done) performed any time in the 12 months prior to study enrolment.
- And one or more of the following guideline based ventricular pacing indications:
  - a) Permanent or intermittent 3rd degree AV block
  - b) Permanent or intermittent Mobitz type II AV block
  - c) First Degree AV block with a pacing indication
  - d) Slow chronic Atrial Fibrillation or Proposed AV node ablation
  - e) Bifascicular block with a pacing indication
  - f) Trifascicular block with a pacing indication
  - g) Wenckebach with a pacing indication

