### **(iii) Secondary Endpoint Analysis**

Secondary outcomes will be analysed using the appropriate generalised linear model depending on the distribution of the outcome, like linear regression for continuous and logistic regression for binary outcomes. When measurements are collected at multiple time points, repeated measurements mixed models will be used. All implant pacing parameters will be recorded including X-ray time as a surrogate for procedure time and pacing thresholds, sensed R wave, impedance and pacing amplitudes. These metrics will be compared between arms.

Quality of life will be assessed over time and treatment groups compared using longitudinal analysis with appropriate recognition for informative dropout, using joint modelling to account for events.

Our planned subgroup analyses will be performed by adding the interaction term between treatment and the subgroup variable into the model.

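### A patient with an ejection fraction of exactly 50% belongs to neither EF set, and baseline subgroups are labelled as per-protocol populations

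*Protocol*

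**What the plan says.** Protocol section 7.3 (i), Analysis populations, makes intention to treat the primary analysis, with every randomised participant kept in the allocated arm. It then says "Per-Protocol (PP) populations will also be defined" and gives one list of twelve sets. Four of them describe patients as they were before treatment:

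- "Those with an EF <50% at enrolment"
- "Those with an EF >50% at enrolment"
- "Those with AF at baseline"
- "Those with complete AV block at baseline"

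Three other places bear on these sets:

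- **Section 3.1 (i), Inclusion criteria:** "Left ventricular ejection fraction >35% from any clinical echocardiogram", so a value of exactly 50% is eligible.
- **Section 7.3 (iii), Secondary Endpoint Analysis:** "Our planned subgroup analyses will be performed by adding the interaction term between treatment and the subgroup variable into the model".
- **Planned Subgroup / Sub-study Analyses, item iii:** pre-implant EF is examined as a predictor of the between-arm difference, with no threshold stated.

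**The concern.** There are two faults, both in wording that the protocol itself fixes.

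First, the two EF sets read as a split of the trial population, but they are not one. Anyone at the cut-point is excluded from both. If the sets are programmed as written, the two EF results will not add up to the randomised total, and someone will later have to decide where the 50% patients go. That decision is best made before outcomes by arm are seen.

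Second, a per-protocol population is defined by the treatment actually received or by adherence to the plan. EF, AF and complete AV block at baseline are neither. Under this label, and mixed with true treatment-received sets, it is unclear whether these groups are to be analysed as randomised or only among patients who received the allocated pacing. Those are different estimates. The label also leaves it uncertain whether the interaction rule in 7.3 (iii) applies to them.

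**Working it through.** The plan states no figure to reproduce here. The check is of set logic, followed by a comparison of sections.

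**1. Coverage of the EF sets.** Inputs: eligible EF > 35% (section 3.1); lower set EF < 50% and upper set EF > 50% (section 7.3 (i)).

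- Covered: 35 < EF < 50, or EF > 50.
- Eligible but not covered: EF = 50.
- Going through whole-number EF values from 36 to 80, 50 is the only value in neither set. With < 50 / ≥ 50, or with ≤ 50 / > 50, no value is left out.

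No other part of the protocol assigns 50% to a side.

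**2. How many patients.** The number is p × 2600, where 2600 is the planned total (section 7.2) and p is the share recorded at exactly 50%. The protocol gives no EF distribution, so p is unknown. As pure illustration:

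| Assumed p | Patients in neither set |
|---|---|
| 1% | 0.01 × 2600 = 26 |
| 5% | 0.05 × 2600 = 130 |
| 10% | 0.10 × 2600 = 260 |
| 15% | 0.15 × 2600 = 390 |

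Nothing in the documents favours one row over another.

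**3. Which analyses still contain them.** The primary analysis includes all randomised participants, so it keeps them. Subgroup item iii has no cut-point as stated, so it keeps them too. The loss is confined to the two EF sets.

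**4. What the per-protocol list contains.** The twelve entries are of three kinds:

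| Kind | Entries | Count |
|---|---|---|
| Treatment received, by adjudication | CSP; His; left bundle; selective His; non-selective His | 5 |
| Mean pacing percentage during the trial | > 20%; > 40%; > 80% | 3 |
| Characteristic at enrolment | EF < 50%; EF > 50%; AF; complete AV block | 4 |

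Only the first kind fits the heading. The pacing-percentage sets do not describe adherence either, but they are measured after randomisation and raise a separate question.

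**5. Comparison with the planned subgroup list.** Its six items are the echo sub-study, percentage of ventricular pacing, pre-implant LV function, pacing type, NHS Digital follow-up and cost-effectiveness. EF is there (item iii). AF and complete AV block are not; they appear as analysis groups only in the per-protocol list. The interaction rule in 7.3 (iii) speaks of planned subgroup analyses, so nothing states that it reaches these two.

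**The case against.** The best defence is that little depends on this. The protocol defers the detail of the analyses to a SAP, where subgroup boundaries are often settled. The EF question already has an analysis that excludes nobody. AF at baseline and complete AV block at baseline are yes/no variables, so each complement is simply the rest of the intention-to-treat population and an interaction can be fitted without listing it. Most of this stands, and it sets the size of the point. It does not remove it: the EF limits and the per-protocol heading are stated in the protocol and stated wrongly. A SAP that copied them would inherit the fault.

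Three stronger readings are tempting and are not supported:

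- **That the listed sets permit only separate within-group tests.** They do not, because the complements can be inferred. What is missing is a clear link to the interaction test.
- **That the EF contrast is a main question of the trial.** None of the objectives in sections 2.1 to 2.3 asks about effect by baseline EF. Section 1.1 justifies enrolling everyone above 35% by equipoise and promises no comparison at 50%.
- **That some hundreds of patients are lost.** Rounded values are plausible because EF comes from routine clinical scans, but the documents give no share at 50%, and these patients are not lost to the trial.

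**Conclusion.** The point holds as a minor correction. As written, an eligible patient with EF recorded at exactly 50% is in neither EF set; this follows from the two strict limits and needs no assumption. The number affected is unknown. EF, AF and complete AV block at baseline are wrongly headed as per-protocol populations, and for AF and complete AV block the protocol does not clearly require the interaction test that it sets for subgroups. The effect is limited to secondary analyses. The primary result, its power and its type I error are unchanged.

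**What to change.** 1. Make one EF limit inclusive, either < 50% / ≥ 50% or ≤ 50% / > 50%. Both close the gap. The documents do not dictate which to use, so choose and record it before outcomes by arm are examined.
2. Move EF, AF and complete AV block from the per-protocol list to the subgroup list. Analyse each in the intention-to-treat population as a two-level variable, tested by the treatment-by-subgroup interaction already specified in 7.3 (iii).
3. State how the two-level EF variable relates to subgroup item iii, which has no cut-point.

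The cost is a wording change in the protocol, carried into the SAP. It needs no new data and no change to the sample size.

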### **(ii) Primary Endpoint Analysis**

Survival curves for primary endpoint will be estimated by Kaplan and Meier and the log-rank test methods. The hazard ratio and respective 95% confidence interval will be computed using the Cox proportional hazards regression model, or appropriate alternative. In secondary analysis the model will be adjusted for clinical important confounders that will be pre-specified in the statistical analysis plan. The underlying assumptions of any fitted model will be assessed as appropriate.

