### **3. STUDY DESIGN**

The PROTECT-HF study will be performed at approximately 40 investigational sites in England, Wales, Scotland, and Northern Ireland, together with approximately 6 international investigational sites. The study will be a multi-centre, prospective, 1:1 randomised, patient-blinded trial with an initial Vanguard Phase to demonstrate safety and feasibility. The primary analysis will be intention to treat. We will also perform an on-treatment analysis.

The trial will include an initial Vanguard Phase to demonstrate safety and feasibility in recruitment. This phase will last 24 months and will aim to meet pre-specified recruitment targets (>80%) with cross-over rate of less than 30% This will be reviewed within the trial steering committee and a decision taken at the time regarding continuation of the trial as is, activation of additional sites or consideration of early termination.

Patients will be identified from clinical services as those requiring cardiac pacing and then invited to participate.

If eligible, informed consent will be obtained. If patient is unable to sign the informed consent form themselves due to blindness or other disability which doesn't affect their understanding of the study/capacity, a witness can sign on behalf of the patient. Where verbal consent is used to consent patient to the trial, randomisation cannot occur until the patient or witness physically signs the informed consent form. Demographic data and medical history information will be collected at screening. Patients will then be randomised following written consent to either standard of care RV pacing - this pacing lead can be placed either apically or septally at the operator's discretion, or to a physiological pacing strategy. Patients will be blinded to the strategy they are allocated. If allocated to a physiological strategy – this can be either His or Left Bundle pacing at the operator's discretion. If physiological pacing cannot be appropriately delivered utilising the initial choice, approach operators must transition to

try the alternative conduction system pacing method i.e. if fail His pacing move to Left bundle pacing if they are trained in the alternate method as well. If neither are successful operators should implant an LV lead to deliver biventricular pacing as this delivers a more physiological approach than standard RV pacing. Crossover to the RV arm would occur if available physiological approaches were attempted and unsuccessful.

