#### 4.3 Randomisation and Blinding

Randomisation will take place using a fully validated, high quality, real-time electronic data capture system (OpenClinica database). Randomisation will be 1:1 between receiving ventricular myocardial pacing from a lead in the Right Ventricle versus a Physiological Pacing approach. Randomisation will occur once a patient has signed the informed consent form. The randomisation list will be programmed by the statistician using variable block length and stratified by site. Patients will be blinded to treatment allocation in a single blinded fashion. All endpoints will be adjudicated by blinded committee of clinicians with expertise in heart failure.

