## **4.7 Follow Up**

Follow up at all UK centres will be conducted by a central trial hub utilising:

1. Online questionnaires and/or telephone contact with the participant or their nominated representative completing questions onto the OpenClinica ePRO database. This will occur every 6 months starting from device implantation.
2. Remote follow-up from a participant's pacemaker where available, downloads will be scheduled every 6 months. Where possible data will be transferred from device companies to the trial team either directly or via the implanting/recruiting centre.
3. For participants residing in England – mortality and hospital statistics will be obtained by data draws every 24 months from nationally held records.

PROTECTHF	Protocol No: 22HH7931	Sponsor: Imperial College London	V9.0 16-Jun- 2025
------------------	--------------------------	-------------------------------------	----------------------

Additionally, the central staff will contact participants if made aware by local study team or by the participant of an adverse events and will follow this up accordingly.

Incidental findings identified as part of the research protocol will be reviewed and reported by the clinical members of the research team. Any incidental findings identified will be communicated to the patient's clinical team as well as their GP as per standard protocol.

In some international centres, patients will be contacted by their local site teams instead of the central trial hub. Some international centres may conduct streamlined follow-up, collecting data on HFH and mortality only. Some international centres may also conduct 1-yearly follow-up instead of 6-monthly follow-up and this may be based on data from a national registry instead of via telephone calls to participants directly.

Participants can withdraw from questionnaire and where this is noted, the applicable participants will be followed up on their medical records only, if participants consents to this. A protocol deviation should be raised where participants want to withdraw from questionnaires.

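### Randomisation is stratified by site, but the primary log-rank test and Cox model as written do not carry site; the test stays valid, and power is lost only if sites differ markedly in event rate

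*Protocol*

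**What the plan says.** **Design.** Protocol section 4.3: "Randomisation will be 1:1 between receiving ventricular myocardial pacing from a lead in the Right Ventricle versus a Physiological Pacing approach". It continues: "The randomisation list will be programmed by the statistician using variable block length and stratified by site". No other stratification factor is named. Section 3 plans "approximately 40 investigational sites in England, Wales, Scotland, and Northern Ireland, together with approximately 6 international investigational sites", so about 46 strata.

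**Primary analysis.** Section 7.3 (ii): "Survival curves for primary endpoint will be estimated by Kaplan and Meier and the log-rank test methods". The hazard ratio and its confidence interval are "computed using the Cox proportional hazards regression model, or appropriate alternative". The section has no site strata, site covariate or site frailty.

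**Adjustment.** The same section adds: "In secondary analysis the model will be adjusted for clinical important confounders that will be pre-specified in the statistical analysis plan". This is the only adjustment it mentions, and the confounder list for that secondary model is the only item it expressly hands to the SAP. The opening of section 7.3 separately leaves a detailed account of all analyses to the SAP, to be finalised before database lock.

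**Follow-up by site.** Section 4.7 runs follow-up at all UK centres from one central hub. It allows exceptions abroad: "Some international centres may also conduct 1-yearly follow-up instead of 6-monthly follow-up and this may be based on data from a national registry". Some international centres may also collect only heart failure hospitalisation and mortality.

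**The concern.** Blocking within site balances the arms inside each site. If sites have different baseline hazards, that balance removes between-site variation from the treatment comparison. An unstratified log-rank test does not take credit for this, because its variance still treats that variation as noise. Its type I error then falls below the nominal 5%, some power is forgone, and the marginal hazard ratio lies slightly closer to 1 than the within-site hazard ratio.

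The stake is efficiency. Type I error is not inflated, and the randomisation is sound either way.

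The protocol gives some reason to think that observed event rates could differ by site. The primary endpoint in section 2.4 includes ambulatory diuretic therapy, yet some international centres may record only hospitalisations and deaths, and some may follow up yearly from a registry. Ascertainment alone could separate those sites from the rest. How far is not stated.

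**Working it through.** **1. The plan's own figure.** Inputs from section 7.1: control event-free probability 0.725 at 4 years, hazard ratio 0.78, two-sided alpha 0.05, power 85%, 3.5 years of recruitment and 3 years of follow-up.

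- Events (Schoenfeld): 4 × (1.960 + 1.036)² / (ln 0.78)² = 35.91 / 0.0617 = 582.
- Control hazard: λ = −ln(0.725)/4 = 0.0804 per year.
- Event probability with uniform accrual: 1 − [exp(−3λ) − exp(−6.5λ)] / (3.5λ) = 0.315 for control and 0.256 for the treated arm (hazard 0.78λ). The mean is 0.2856.
- Total: 582 / 0.2856 = 2038. Freedman's formula (588 events) gives 2059. The plan states 2048, at which power is 85.2%.

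The stated figure reproduces within 1%. It contains no site term and needs none.

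**2. What a given site spread means.** The between-site SD of the log hazard is not in the documents, so a range is assumed. If 27.5% is taken as a typical site's 4-year control rate, a site one SD above or below has rate 1 − 0.725^exp(±SD):

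| SD | Hazard ratio, +1 SD site v −1 SD site | 4-year rate, −1 SD site | 4-year rate, +1 SD site |
|---|---|---|---|
| 0.35 | exp(0.7) = 2.0 | 20% | 37% |
| 0.5 | exp(1.0) = 2.7 | 18% | 41% |
| 0.7 | exp(1.4) = 4.1 | 15% | 48% |

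**3. Simulation at N = 2048.** Hazard ratio 0.78 or 1; 46 sites of unequal size; permuted blocks of 4 or 6 within site; normal site effects on the log hazard; marginal control rate held at 27.5% at 4 years; 8000 runs per setting, with both tests applied to the same data sets. Number of sites, block sizes, site-size spread and SD are assumptions. The Monte Carlo standard error is about 0.2 points for type I error and 0.4 points for power.

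| Site SD | Type I error, unstratified | Type I error, stratified | Power, unstratified | Power, stratified |
|---|---|---|---|---|
| 0 | 5.0% | 5.0% | 85.3% | 84.9% |
| 0.2 | 4.8% | 5.0% | 85.7% | 85.5% |
| 0.3 | 5.0% | 5.4% | 84.8% | 85.3% |
| 0.5 | 4.0% | 4.9% | 83.4% | 84.9% |
| 0.8 | 3.0% | 4.8% | 78.7% | 84.4% |

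Up to SD 0.3 the power differences are under half a point in either direction, about one Monte Carlo standard error.

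**4. Second simulation at the planned N = 2600.** With 46 sites and 3000 runs per setting, there was no detectable loss at SD 0.35 or below. Unstratified against stratified power was 83.3% v 84.6% at SD 0.5 and 80.0% v 84.2% at SD 0.7.

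**5. Size in patients.** Required sample size scales with (1.960 + z_power)². At SD 0.5, 84.9% against 83.4% power gives (1.960 + 1.032)² / (1.960 + 0.970)² = 8.95 / 8.58 = 1.04, or about 4% of the sample size.

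**6. Why stratifying costs little.** 2600 / 46 is about 57 patients per site on average. At an event probability of 0.2856 that is about 16 events per site, so most strata are informative.

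**The case against.** The strongest objection is that this reads a decision into silence. Section 7.3 (ii) never says that the test is unstratified, it allows an alternative to the Cox model, and section 7.3 sends analytic detail to the SAP, where strata and pooling rules are commonly fixed. This stands in part: the protocol does not rule out stratification, and the SAP may already provide it. But the protocol is not silent on where adjustment belongs. It assigns adjustment to a secondary analysis, so a SAP that followed the text literally would leave site out of the primary one.

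Second, nothing here is invalid. An unstratified log-rank test after site-blocked randomisation does not inflate type I error, and the marginal hazard ratio is a different estimand, not a wrong one. This stands in full.

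Third, a reader might infer from the international follow-up arrangements that large site differences are to be expected. The documents do not support that. The exceptions concern some of about 6 of the 46 or so sites, UK follow-up runs through one hub, and endpoints are adjudicated centrally by a blinded committee. Differences are plausible, but nothing in the protocol points to an SD of 0.5 or more.

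Fourth, the remedy is not free: it needs a pooling rule and costs a little if sites are alike. This also stands, and the cost is small.

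**Conclusion.** The mismatch is real and minor. Site is the only randomisation stratum, and the primary analysis as written does not carry it.

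The loss depends on a quantity that the documents do not give. It is undetectable at a between-site SD of 0.35 or below, about 1.5 points of power at 0.5 and about 4 points at 0.7. These figures rest on about 46 sites, small blocks, normally distributed site effects and a marginal control rate of 27.5%.

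Two stronger readings should be resisted. A reader might infer that leaving out site makes the test conservative in any case. It does not: without site differences the simulated error rate is 5.0%, and a clear shortfall appears only from about SD 0.5, where it is 4.0%. A reader might also infer that the sample size is wrong. It is not: 2048 reproduces within 1%.

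**What to change.** In section 7.3 (ii), state that the primary log-rank test and Cox model are stratified by site, and that very small sites are pooled (for example by country) under a rule fixed before unblinding. Keep the unstratified log-rank test and Cox model as a sensitivity analysis. If the SAP already specifies this, align 7.3 (ii) with it.

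The cost is one sentence and a pooling rule. If sites do not differ, about half a power point is lost (84.9% against 85.3% at SD 0). The reported hazard ratio becomes a within-site one, which should be said when it is presented. The sample size need not change.
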